## 5 STATISTICAL METHODS

Descriptive statistics will be reported for continuous variables using mean, standard deviation (SD), median, minimum and maximum. Categorical variables will be summarized using frequency count as number (percentage) of subjects. Graphical displays of the data might be presented where appropriate to aid interpretation.

### 5.1 STUDY ENDPOINTS

#### 5.1.1 Primary Endpoint(s)

The primary efficacy endpoint is the proportion of subjects who do not require a platelet transfusion or any rescue procedure for bleeding after randomization and up to 7 days following an elective procedure.

#### 5.1.2 Secondary Endpoint(s)

The secondary efficacy endpoints are:

- Proportion of responders defined as subjects who achieve platelet counts of  $\geq 50 \times 10^9/L$  on Procedure Day (i.e., prior to receiving a platelet transfusion or undergoing the elective procedure)
- Change from baseline in platelet count on Procedure Day (i.e., prior to receiving a platelet transfusion or undergoing the elective procedure)

#### 5.1.3 Exploratory Endpoint(s)

The exploratory endpoints are:

- Platelet count and change from baseline in platelet count at each visit
- Proportion of responders defined as subjects who achieve platelet counts of  $\geq 50 \times 10^9/L$ ,  $\geq 75 \times 10^9/L$ , or  $\geq 200 \times 10^9/L$  at each visit
- Number of platelet units used per platelet transfusion episode
- Severity of bleeding event assessed by WHO bleeding score and Bleeding Academic Research Consortium (BARC) bleeding scale
- Proportion of subjects with a WHO bleeding score  $\geq 2$  after randomization and up to 7 days following an elective procedure
- Health economics assessed by resource use

## 5.2 STUDY SUBJECTS

### 5.2.1 Definitions of Analysis Sets

Full Analysis Set (FAS): The FAS is the group of all subjects who are randomized into the study.

Per Protocol Analysis Set (PP): The PP is the group of all randomized subjects who receive protocol-assigned study drug and do not meet any of the following criteria:

- Baseline platelet count of  $>50 \times 10^9/L$
- Subjects who were enrolled in the study despite not being planned for transfusion even in the event of no significant increase of platelet count
- Taking prohibited prior medications or prior transfusion
- Presence of significant bleeding at baseline
- Did not have a protocol permitted procedure on Day 8 - 15
- Received dose different from the intended dose
- Received  $<80\%$  of the total dose or received  $>40\%$  of total dose without food
- No elective procedures or elective procedure outside day 8-15
- Subject received platelet transfusion before knowing V4 platelet count
- Subject refused platelet transfusion

Subjects who met any of the criteria listed above will be excluded from the PP due to possible introduction of bias.

Safety Analysis Set: The Safety Analysis Set is the group of subjects who receive at least one dose of study drug and have at least one post dose safety assessment.

The number (percentage) of subjects in each analysis set will be summarized by treatment groups using descriptive statistics. The summaries for FAS and PP will be based on subjects “as randomized”. The summary for Safety Analysis Set will be based on subjects “as treated”.

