9.4.7.3 Prohibited Concomitant Therapy

Erythropoietin stimulating agents are prohibited throughout the study. Interferon use is prohibited during the study; however, at the investigator's discretion, subjects may restart IFN therapy if clinically indicated during the Follow-up Phase (ie, after Visit 4 [Procedure Day]).

Eltrombopag, romiplostim, heparin, warfarin, NSAIDs, aspirin, verapamil, estrogen, and antiplatelet therapy with ticlopidine or glycoprotein IIb/IIIa antagonists (eg, tirofiban) are prohibited. (revised per Amendment 02) Aspirin, for antiplatelet therapy, can be prescribed at the discretion of the investigator in subjects in which the platelet count rises and who are believed to have an increased risk of thrombosis. In subjects where use of aspirin is contraindicated, an alternate antiplatelet therapy such as a platelet adenosine diphosphate receptor inhibitor (eg, clopidogrel) can be prescribed. It should be noted that clopidogrel should be used with due consideration in subjects with liver disease. Lack of activation due to liver disease could lead to a reduction in activation of the prodrug. In addition, as clopidogrel is activated by the CYP system, care is required when administering clopidogrel to subjects with liver disease and co-administering clopidogrel with agents that are substrates or inhibitors of CYP.

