9.7.1.2 Definitions of Analysis Sets

Full Analysis Set (FAS): The FAS is the group of randomized subjects. The FAS will be analyzed “as randomized”.

Per Protocol Set (PP): The PP Set is the group of all randomized subjects who receive protocol-assigned study drug and do not meet any of the following criteria:

- Subjects who have any major protocol violations (major inclusion/exclusion violations or other major protocol violations that impact the evaluation of efficacy)
- Subjects who use a prohibited concomitant medication that affects the assessment of study endpoints
- Subjects who are noncompliant in terms of study medication

A comprehensive list of subjects to be excluded from the PP will be agreed upon by the study team prior to database lock. The PP will be analyzed “as randomized”.

Safety Analysis Set: The Safety Analysis Set is the group of subjects who receive at least 1 dose of study drug and have at least 1 postdose safety assessment. This set will be analyzed “as treated.”

PK Analysis Set: The PK Analysis Set is the group of randomized subjects who receive at least 1 dose of avatrombopag and have at least 1 quantifiable avatrombopag concentration with a documented dosing history.

PK/PD Analysis Set: The PK/PD Analysis Set is the group of randomized subjects who receive at least 1 dose of avatrombopag, have at least 1 quantifiable avatrombopag concentration, and at least 1 platelet count, with a documented dosing history.

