### 5.2.3 Protocol Deviations

Major protocol deviations will be identified, reviewed and documented by the clinical team prior to database lock/treatment unblinding. All protocol deviations will be categorized according to standard classifications including the following:

- Violations of inclusion/exclusion criteria
- Noncompliance with protocol procedures/assessments
- Noncompliance of drug dosage
- Use of prohibited treatments

All significant protocol deviations will be listed, and summarized by category and by treatment group.

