### 5.2.5 Prior and Concomitant Therapy

All investigator terms for medications recorded on the CRF will be coded using the WHO Drug Dictionary (WHO DD).

Prior medications are defined as medications that stop prior to the first dose of study drug. Concomitant medications are defined as medications that (1) start before the first dose of study drug and are continuing at the time of the first dose of study drug, or (2) start on or after the date of the first dose of study drug, up to 30 days after the last dose of study drug.

The number (percentage) of subjects who take prior and concomitant medications will be summarized using the Safety Analysis Set by treatment group, Anatomical Therapeutic Chemical (ATC) Classification, and WHO DD preferred term. In addition, the number (percentage) of subjects who take the concomitant medications associated with elective procedures will also be summarized using the Safety Analysis Set by treatment group, ATC Classification, and WHO DD preferred term.

If a subject takes the same medications for the same class level or drug name, the subject will be counted only once for that class level or drug name.

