## 7 CHANGES IN THE PLANNED ANALYSES

SAP version (Final 2.0) is updated based on Protocol Amendment 04 with the following changes:

- Sections 3.1.2, 3.1.3, 5.1.2, 5.1.3, 5.3.3.1, 5.4.2, 5.4.2.3, 5.4.3 and 5.4.3.5: Efficacy endpoint "Proportion of subjects with a WHO bleeding score  $\geq 2$  after randomization and

up to 7 days following an elective procedure” is moved from secondary to exploratory endpoint to match the protocol amendment 4. These sections have been updated to reflect this change.

- Section 4: Sample size is reduced from 300 to 200. This section has been updated to match the protocol amendment 4.
- Section 5.4.2.2: Calculation of 95% CI for change from baseline in platelet count on Procedure Day for each treatment group within each baseline platelet count cohort has been removed to ensure consistency with the study objectives.
- Section 5.7.1: This section is updated to reflect that only listings will be provided for the Health Economics Assessment.
- Section 5.2.1: Per-Protocol exclusion criteria are finalized.

SAP version (Final 2.0) is also updated based on Protocol Amendment 02 with the following changes:

- Section 3.2 table 1, and sections 5.2.4, 5.3.2, 5.3.4, 5.4.1, 5.4.1.2 and 5.4.2.1: Categorization of risk of bleeding is updated to match protocol amendment 02
- Section 5.6.6.3: Listing of platelet function test assessed using platelet aggregometry has been added.
- Section 13.1: "Fasting Glucose value" has been added to the criteria for determining grade 3 and 4 in the lab grading table.

SAP version (Final 2.0) is also updated from version Final 1.0 to ensure consistency with the eCRF/protocol as follows:

- Section 5.6.5: ECG interpretation category is updated.
- Section 5.2.4: Baseline summaries of creatinine clearance and disease etiology, and subgroup analysis by disease etiology have been added.

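### The SAP's finalized Per Protocol exclusion list omits the protocol's criterion on prohibited concomitant medication (minor; PP sensitivity analysis of the primary endpoint only)

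*SAP*

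**What the plan says.** **Protocol.** Section 9.7.1.2, like the Synopsis, defines the PP set by three exclusions. One is "Subjects who use a prohibited concomitant medication that affects the assessment of study endpoints". Another covers major eligibility violations and "other major protocol violations that impact the evaluation of efficacy". The third is noncompliance with study medication. The study team agrees the list of excluded subjects before database lock.

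Section 9.4.7.3 names the prohibited drugs, beginning "Eltrombopag, romiplostim, heparin, warfarin, NSAIDs, aspirin, verapamil, estrogen, and antiplatelet therapy". It then adds: "Aspirin, for antiplatelet therapy, can be prescribed at the discretion of the investigator in subjects in which the platelet count rises" and who are thought to be at raised thrombotic risk. Where aspirin is contraindicated, another antiplatelet agent may be used.

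**SAP.** Section 5.2.1 replaces the three exclusions with ten specific ones. The only medication item is "Taking prohibited prior medications or prior transfusion". Section 5.2.5 states: "Prior medications are defined as medications that stop prior to the first dose of study drug", and defines concomitant medication separately. Section 5.2.3 has "Use of prohibited treatments" as a deviation category, to be reviewed before lock, listed and summarized. Section 7 records the change as "Per-Protocol exclusion criteria are finalized", with no reason for dropping the protocol item.

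Sections 5.3 and 5.4.1.1 use the PP set only to repeat the primary analysis as a sensitivity analysis.

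**The concern.** A PP analysis asks whether the result holds among subjects whose outcome reflects the assigned treatment as planned. Taking a prohibited drug that acts on the outcome is a standard reason to leave that set, and the protocol says so. The SAP keeps the restriction for drugs stopped before first dose, yet has none for drugs taken while the endpoint is accruing.

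The omission is not purely formal. Amendment 02 prohibited eltrombopag and romiplostim because they are used off-label in this setting. Both are thrombopoietin receptor agonists and could raise the platelet count that guides transfusion. Other prohibited drugs could act on bleeding instead.

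At stake is whether the PP analysis follows the protocol's definition of the set, and whether any later repair can be shown to have been decided without sight of the data.

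**Working it through.** **Step 1. Compare the definitions.**

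| Situation | Protocol 9.7.1.2 | SAP 5.2.1 |
|---|---|---|
| Prohibited drug stopped before first dose | Excluded if a major violation | Excluded by name |
| Prohibited drug on study, affecting endpoints | Excluded by name | No item |
| Other major violation affecting efficacy | Excluded by general item | No general item |

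The other nine SAP items concern baseline platelet count, no plan to transfuse, bleeding at baseline, the procedure and its timing (two items), dose received, amount taken and food, transfusion before the Visit 4 count is known, and refusal of transfusion. None covers on-study medication. The SAP defines PP as all randomized subjects who receive their assigned drug and meet none of the ten items, so a subject outside the list is in the set.

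**Step 2. Check the baseline item.** SAP 5.2.1 excludes a baseline count above 50. Protocol 9.3.1 requires the mean of the Screening and Baseline counts to be below 50.

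- A mean of exactly 50 is ineligible but is not excluded by the SAP item.
- The SAP item does not say mean, and SAP 8.1 sets the Baseline visit as the last on or before Day 1. If that single value were used, Screening 44 and Baseline 52 (mean (44 + 52)/2 = 48, eligible) would be excluded.

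Replacing the sign alone would not cure this.

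**Step 3. Reproduce the design figure.** Inputs from SAP 4, per cohort: 67 avatrombopag and 33 placebo; 18% placebo response; a 35-point difference, hence 53% on avatrombopag; Fisher's exact test, two-sided 0.05. Summing binomial probabilities over all tables with P ≤ 0.05 gives power of 92.6%, consistent with the stated figure of more than 90%. The concern does not alter it.

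**Step 4. Illustrate the effect of one subject.** 0.53 × 67 = 35.5 and 0.18 × 33 = 5.9, so take 36/67 and 6/33 as the reference: 53.73 − 18.18 = 35.55 points.

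(a) A prohibited drug turns one would-be failure into a success:

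| Arm | Kept in PP | Excluded from PP | Kept minus excluded |
|---|---|---|---|
| Placebo | 36/67 − 7/33 = 32.52 | 36/67 − 6/32 = 34.98 | −2.5 |
| Avatrombopag | 37/67 − 6/33 = 37.04 | 36/66 − 6/33 = 36.36 | +0.7 |
| One in each | 37/67 − 7/33 = 34.01 | 36/66 − 6/32 = 35.80 | −1.8 |

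(b) A prohibited drug turns one would-be success into a failure:

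| Arm | Kept in PP | Excluded from PP | Kept minus excluded |
|---|---|---|---|
| Placebo | 36/67 − 5/33 = 38.58 | 36/67 − 5/32 = 38.11 | +0.5 |
| Avatrombopag | 35/67 − 6/33 = 34.06 | 35/66 − 6/33 = 34.85 | −0.8 |

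For the reference and the scenarios in (a), Fisher's exact P lies between 0.0005 and 0.0025. These P values are illustrative only: the planned PP test is the Cochran-Mantel-Haenszel test stratified by bleeding risk. The denominators are also the full cohort, not a PP set already reduced by the other criteria.

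**The case against.** **Process may catch it.** The protocol has the study team agree the PP exclusions before lock, and SAP 5.2.3 has major deviations, including use of prohibited treatments, reviewed before lock and unblinding. This is a real mitigation. It means that saying such a subject stays in PP describes the text, not a settled consequence. But SAP 5.2.3 does not link that category to PP membership, and SAP 5.2.1 gives the team no criterion to apply.

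**The protocol criterion is itself a judgement.** Whether a drug affects endpoint assessment would still be decided case by case. That stands, but a judgement under a stated criterion before unblinding is better than one under none.

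**A reader might infer that the early-transfusion exclusion is also an error.** It has no exception for platelets given as rescue for bleeding, which the protocol permits and counts as a failure, so it could remove a subject because of an outcome. The documents do not support calling this wrong. No passage requires a bleeding exception in PP, the SAP gives possible bias as its reason for the exclusions, and the Full Analysis Set keeps these subjects as failures. Such cases should also be rare: clinically significant active bleeding is an entry exclusion, and Amendment 04 reports fewer bleeding events than expected. A clarification would help but is optional.

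**Conclusion.** The inconsistency is real and minor. The protocol states a PP exclusion for prohibited concomitant medication; the SAP's finalized list lacks it, has no general item that could stand in for it, and gives no reason.

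Only the PP sensitivity analysis of the primary endpoint is affected. A reader might infer that the primary conclusion is at risk. It is not: the primary test uses the Full Analysis Set, and the requirement of significance in both cohorts and the other three sensitivity analyses do not use PP.

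The size and direction of any effect are unknown and probably small. The documents do not say how many subjects took prohibited drugs, in which arm, or with what effect. The one-subject shifts of about 0.5 to 2.5 points rest on planned cohort sizes and design response rates, and their sign depends on the arm and on what the drug does.

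**What to change.** Amend SAP 5.2.1 before database lock:

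1. Add the protocol's exclusion for prohibited concomitant medication that affects endpoint assessment. Reconcile it with protocol 9.4.7.3, which lists aspirin as prohibited yet allows antiplatelet use at the investigator's discretion, by stating that use allowed there does not by itself remove a subject from PP. This concerns set membership only and changes no clinical rule.
2. Word the baseline item as mean baseline platelet count ≥50 × 10⁹/L, to match protocol 9.3.1.
3. Optional: state whether a platelet transfusion recorded as rescue for bleeding before the Visit 4 count is known triggers exclusion, and report by arm and cohort how many subjects the early-transfusion item removes.

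The cost is SAP wording and, if item 3 is adopted, one line of counts. No new data are needed: concomitant medications, platelet counts, and rescue procedures with dates and times are already collected. After unblinding, the same edit could look data-driven.

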Study E5501-G000-202 evaluated the efficacy, safety, and population PK of once-daily oral avatrombopag dosing, in subjects with chronic liver diseases and thrombocytopenia prior to elective surgical or diagnostic procedures. The primary efficacy endpoint was the proportion of responders with platelet count increases from baseline of $\geq 20 \times 10^9/L$ and a platelet count of $\geq 50 \times 10^9/L$ once from Day 4 through Day 8. The proportion of responders for all avatrombopag-treated subjects was 48.4% compared with 8.1% in the combined placebo group ($P < 0.0001$). All doses of avatrombopag achieved a significantly higher proportion of responders compared with their respective cohort placebo arms and the highest platelet count responses were observed between Days 10 to 14 after first dose. In addition, avatrombopag appeared well tolerated in this patient population. There was no clear trend regarding the incidences of AEs between placebo and avatrombopag treatment groups, and the commonly reported treatment-emergent adverse events (TEAEs) and serious TEAEs were consistent with the disease state of the patient population. The findings from Study E5501-G000-202 suggest that avatrombopag would be an effective therapy for the treatment of thrombocytopenia in patients with chronic liver disease, prior to an elective procedure.

For more detailed information regarding effects in humans, please refer to the Investigator Brochure.

7.1.2.4 Common Serious Adverse Events Expected to Occur in the Study Population Even in the Absence of Study Drug Exposure

Thrombotic/thromboembolic complications may occur in patients with chronic liver disease. Portal vein thrombosis (PVT) is of particular concern in chronic liver disease patients who are prone this type of thrombosis and is often associated with poor portal vein flow. The presence of thrombocytopenia can increase the potential for bleeding, which results in an elevated morbidity and mortality risk in patients with liver disease. In cirrhotic patients undergoing abdominal surgery, bleeding accounts for up to 60% of all causes of death. Thrombocytopenic patients often require multiple platelet transfusions, which can be associated with complications such as systemic infections, iron overload, and platelet refractoriness.⁴

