9.1.2.3 Procedure Day (Visit 4)

This will occur 5 to 8 days after the last dose of study drug (on Study Day 10 to 13).

All Procedure Day assessments are to be completed prior to the procedure and include assessments shown in [Section 9.5.2.1 \(Table 5\)](#).

In addition, all subjects are required to return study drug and the dosing diary at this visit.

The elective procedure for those subjects whose preprocedural platelet count is $>200 \times 10^9/L$ on Visit 4 (Procedure Day) may be delayed at the discretion of the investigator until platelet counts are below $200 \times 10^9/L$. All subjects whose platelet count exceeds $200 \times 10^9/L$ will be required to have a Doppler assessment at Visit 5. For any subjects where the presence of a PVT is suspected, confirmation of diagnosis, via CT scan or MRI, should be performed and treatment for PVT initiated per local guidelines.

Permitted procedures and the risk of bleeding associated with each procedure are listed in [Table 1](#). It is planned that no fewer than 10% of subjects will be enrolled into the high risk group and no more than 60% of subjects in the low-risk group.

Table 1 Permitted Procedures and the Risk of Bleeding Associated with Each Procedure (revised per Amendment 02)

Risk of Bleeding Associated with Procedure	Procedure
Low risk	Paracentesis
	Thoracentesis
	Gastrointestinal endoscopy with or without plans for biopsy, colonoscopy, polypectomy, or variceal banding
Moderate risk	Liver biopsy
	Bronchoscopy with or without plans for biopsy
	Ethanol ablation therapy or chemoembolization for HCC
High risk	Vascular catheterization (including right side procedures in subjects with pulmonary hypertension)
	Transjugular intrahepatic portosystemic shunt
	Dental procedures
	Renal biopsy
	Biliary interventions
	Nephrostomy tube placement
	Radiofrequency ablation
	Laparoscopic interventions

Level of risk based on KOL input and Malloy PC, Grassi CJ, Kundu S, Gervais DA, Miller DL, Osnis RB, et al. for the Standards of Practice Committee with Cardiovascular and Interventional Radiological Society of Europe (CIRSE) Endorsement. Consensus Guidelines for Periprocedural Management of Coagulation Status and Hemostasis Risk in Percutaneous Image-guided Interventions (2009)¹⁵

Subjects who have an International Normalization Ratio (INR) >1.6 should be treated with fresh frozen plasma (FFP) or other appropriate therapies, where indicated, as per local guidelines and practices.

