9.4.4 Selection of Doses in the Study

Dose selection has been carefully focused on seeking to maintain an appropriate risk:benefit ratio balance in this patient population, removing the requirement for platelet transfusion, or any rescue procedure for bleeding, while minimizing the risk of thromboembolic events. The selected doses, based on modeling and simulation of the E5501-G000-202 study data, are aimed at achieving sufficient efficacy (eliminating the need for platelet transfusion) while specifically limiting the proportion of subjects achieving platelet counts $>200 \times 10^9/L$ to less than 2%.

The current study design employs a dosing regimen according to baseline platelet count that is anticipated to lead to a similar overall rise in platelet counts irrespective of baseline platelet count.

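### The Per Protocol timing rule (Day 8-15) is not reconciled with the permitted, open-ended delay for platelet counts above 200 × 10⁹/L, so it can remove adherent subjects because of their response

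*SAP*

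**What the plan says.** SAP 5.2.1 lists ten criteria that remove a randomized subject from the PP set. Two concern procedure timing and overlap: "Did not have a protocol permitted procedure on Day 8 - 15" and "No elective procedures or elective procedure outside day 8-15". Neither carries an exception, and the list closes with "Subjects who met any of the criteria listed above will be excluded from the PP due to possible introduction of bias".

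Protocol 9.1.2.3 schedules the procedure as follows: "This will occur 5 to 8 days after the last dose of study drug (on Study Day 10 to 13". For a subject whose count before the procedure at Visit 4 is above 200 × 10⁹/L, it adds that the procedure "may be delayed at the discretion of the investigator until platelet counts are below" 200 × 10⁹/L. The same permission appears in the protocol synopsis, protocol 7.2.1 and 9.1, and SAP 3.2. None of these places gives a latest day.

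Two further places bear on the point:

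- SAP 8.1 runs the Visit 4 analysis window, for subjects who have a procedure, up to the day the procedure was actually done.
- Protocol 9.7.1.2 excludes from PP "Subjects who have any major protocol violations (major inclusion/exclusion violations or other major protocol violations that impact the evaluation of efficacy", together with users of relevant prohibited medication and subjects noncompliant with study drug.

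The FAS is the primary population. PP is supportive and is the first of four listed sensitivity analyses of the primary endpoint (SAP 5.3 and 5.4.1.1).

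**The concern.** A PP set is informative when its exclusions reflect departures from the protocol. Here a subject can do exactly what the protocol allows and still be excluded. The event that starts the chain is a platelet count measured after randomization, and a count above 200 × 10⁹/L is itself an effect of treatment. Such subjects are also the least likely to need a prophylactic transfusion, because inclusion criterion 3 ties the expected transfusion to the absence of a clinically significant platelet rise.

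Removing them selects on response, in effect in one arm. A list justified by avoiding bias would introduce some. If PP and FAS results then differed, the gap could not be attributed cleanly to non-adherence.

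**Working it through.** **1. The passages side by side**

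| Place | Treatment of a procedure after Day 15 following a Visit 4 count above 200 × 10⁹/L |
|---|---|
| Protocol 9.1.2.3, SAP 3.2 | Permitted; no latest day |
| SAP 8.1 | Accommodated; Visit 4 window ends on the actual day of the procedure |
| Protocol 9.7.1.2 | Not among the stated grounds for PP exclusion |
| SAP 5.2.1 | Excluded from PP, no exception |

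**2. Room for a delay.** Visit 4 falls on Day 10 to 13 and the PP window closes on Day 15. The slack is 15 − 13 = 2 days to 15 − 10 = 5 days. In Phase 2, "the highest platelet count responses were observed between Days 10 to 14 after first dose" (protocol 7.1.2.3), so Visit 4 may sit near the peak. A delay past Day 15 is plausible. The documents give no figure for how likely it is.

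**3. Why the trigger is nearly arm-specific.** Entry requires a mean count below 50 × 10⁹/L with neither value above 60. Passing 200 needs more than 200/60 = 3.3 times the highest permitted single value and more than 200/50 = 4 times the mean baseline. Protocol Table 5 requires hematology before any platelet transfusion, so a transfusion should not produce the Visit 4 value.

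**4. Reproducing the plan's own figure.** Inputs from protocol 9.7.2: 67 avatrombopag and 33 placebo subjects per cohort, placebo rate 18%, difference 35 points (hence 53%), Fisher's exact test, two-sided α = 0.05. Exact enumeration over the two binomials gives 92.6% power, consistent with the stated value above 90%.

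**5. Upper bound on the loss.** Protocol 9.4.4 describes the doses as "specifically limiting the proportion of subjects achieving platelet counts $>200 \times 10^9/L$ to less than 2" percent. Let f be the fraction of avatrombopag subjects above 200. Assume all of them are delayed past Day 15 and all are responders. Then

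PP rate = (0.53 − f)/(1 − f), and PP difference = PP rate − 0.18.

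| f | Lost per cohort (67f) | PP rate | PP difference |
|---|---|---|---|
| 1% | 0.7 | 52.5% | 34.5 points |
| 2% (protocol ceiling) | 1.3 | 52.0% | 34.0 points |
| 5% (assumption) | 3.4 | 50.5% | 32.5 points |
| 10% (assumption) | 6.7 | 47.8% | 29.8 points |

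At f = 2% the chance that at least one avatrombopag subject exceeds 200 is 1 − 0.98⁶⁷ = 74% in a cohort and 1 − 0.98¹³³ = 93% across the trial. This is the chance of meeting the trigger, not of being delayed past Day 15.

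**6. In whole subjects, within one cohort.** Expected responders are 0.53 × 67 = 35.51. Dropping k of them gives a rate of (35.51 − k)/(67 − k):

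| k | PP rate | Fisher power against 33 placebo subjects at 18% |
|---|---|---|
| 0 | 53.0% | 92.6% |
| 1 | 52.3% | 92.2% |
| 2 | 51.6% | 90.0% |
| 3 | 50.8% | 89.0% |

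**The case against.** The strongest case on the other side is that a common procedure window after a five-day course is a recognisable PP choice, that Day 8-15 already widens the planned Day 10-13 by two days on each side, and that the consequence is minimal. Most of this stands. PP has no part in the testing sequence (SAP 5.3.3). The FAS keeps these subjects, and of the other three sensitivity analyses none uses the PP set. The bias in this subset runs against avatrombopag, so it cannot create a false positive. Protocol 9.7.1.2 also has the list of excluded subjects agreed before database lock. That helps only in part, because SAP 7 describes the criteria as finalized.

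A reader might infer several stronger things that the documents do not support:

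- *That PP drops the strongest responders as a group.* Exclusion needs a Visit 4 count above 200, an investigator who chooses to delay, and a procedure after Day 15. A subject above 200 who is not delayed, or is done by Day 15, is not removed by this rule.
- *That delays will often pass Day 15.* No rate of decline and no frequency of delay is given. The Phase 2 timing says when counts were highest, not how long they stayed above 200. Phase 2 also used a loading dose that this trial does not (protocol 7.1), and protocol 7.2.1 expects the elevations to be transient.
- *That the timing criteria as a whole bias PP in one direction.* They also remove subjects in either arm with no procedure or one off schedule for other reasons. The net direction cannot be determined from the documents.
- *That the SAP calls these subjects violators.* It does not; its stated reason is possible bias.

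None of this explains why a delay that the protocol permits, and that SAP 8.1 accommodates, should remove a subject from PP.

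**Conclusion.** The point holds as a narrow inconsistency. The PP timing criteria and the permitted delay are not reconciled, and a subject who adheres to the protocol can be excluded on a post-randomization response expected almost only on avatrombopag. For that subset the bias is against avatrombopag and is confined to the supportive PP analysis.

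At the protocol's 2% ceiling it costs at most about one point per cohort in the expected PP response rate. That bound rests on three assumptions: the share above 200 is at the ceiling, every such subject is delayed past Day 15, and every one is a responder. The ceiling is a modelling target and could be exceeded, which is why the 5% and 10% rows are shown. The true effect may be zero. This is a desirable correction, not one on which the trial's conclusion depends.

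**What to change.** Before database lock and unblinding, add the same clause to both timing criteria in SAP 5.2.1: *except where the procedure was delayed as permitted by protocol 9.1.2.3 because the Visit 4 platelet count exceeded 200 × 10⁹/L*. The count that triggered the delay should be read from the scheduled Visit 4 local result. For a subject with a procedure and no transfusion, SAP 8.1 takes the last visit before the procedure, which after a delay may be a later count.

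If the sponsor prefers to keep the strict window, the alternative is to state that choice and add a PP sensitivity analysis that retains these subjects.

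The cost is one clause in two bullets. It needs no additional subjects, and local platelet counts with their collection times are already recorded. No change to the clinical delay rule is proposed.
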